## **2.0 Objective(s)**

### **2.1 Primary Objective**

**Aim 1.** Determine the feasibility of an 8-week (3x/week) exercise training progression (EX) coupled with the consumption of beetroot juice (BR+EX) prior to exercise in postmenopausal women. Prior work supports daily, short-term (21 days) consumption of beetroot juice in men and women aged 62 +/- 1 years, yet this was performed in the absence of exercise training. Research unequivocally supports the utility of exercise training, still in the context of this proposal, feasibility is unknown.

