#### **3.2 Secondary Outcome Measures**

**2a.** The distance (feet) covered during a 6-minute walk test at baseline prior to the intervention and following BR+EX is the main secondary outcome of interest. To confirm the relationship of the functional 6-minute walk test to aerobic fitness, measures of oxygen consumption (ml/kg/min or L/min), heart rate (bpm), and blood pressure (mm Hg) will be taken during constant speed walking at a typical walking pace prior to the 6-minute walk test. Additionally, functional mobility will be assessed by analyzing triaxial movement patterns from an accelerometer worn on the non-dominant hip during the 6-minute walk test.

The BR+EX intervention will be considered successful in the event that there is a statistically significant increase in 6-minute walk distance (feet) along with a decrease in oxygen consumption (ml/kg/min or L/min), decrease in exercising heart rate (bpm), improvement in heart rate recovery following exercise (post exercise heart rate – heart rate 1 min, 2 min after exercise (bpm)), decrease in exercising blood pressure (mm Hg), decrease in post-exercise blood pressure (mm Hg), and/or improvement in gait function (i.e. preferred walking speed, center of mass characteristics) from baseline to post-intervention above any improvement seen in EX.

**2b.** Percent changes in brachial artery diameter (%), cutaneous vascular conductance (%), and pulse wave velocity (m/s) at baseline prior to the intervention and following BR+EX are secondary outcomes of interest, representing changes in endothelial dependent vasodilation. A non-invasive technique of flow mediated dilation of the brachial artery using ultrasound imaging will be used to assess the percent change in vessel diameter following occlusion. A local heating protocol using non-invasive Laser Doppler flowmetry in conjunction with blood pressure measurements will be used to obtain measures of red blood cell (RBC) flux and mean arterial pressure (MAP) to calculate cutaneous vascular conductance (RBC flux/ MAP). The velocity of the pulse wave traveling from the carotid to femoral artery will be assessed non-invasively using tonometry.

A statistically significant increase in the percent change in brachial artery diameter (%), cutaneous vascular conductance (%), and/or a decrease in pulse wave velocity (m/s) in BR+EX above any improvement observed in EX from baseline to post-intervention will be considered a successful outcome.

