## 5.0 Study Design

To fulfill the purposes outlined above, a 2-arm randomized controlled study design will be employed. After completing initial screening procedures (**screening visit**), subjects will return

to the School of Public Health at Indiana University Bloomington to have baseline measures of weight, body composition, bone density, heart rate, cutaneous vascular conductance, blood pressure, assessed prior to and 3-hours following ingestion of beetroot juice (**Visit 1**). During this visit, two questionnaires will be administered to obtain information related to the health history, physical activity habits, mood state, and cognitive abilities of the subjects. Following a minimum 7-day washout period, to mitigate the risk of any carry-over effect from the acute dose of beetroot juice administered during the initial visit, subjects will have their blood drawn at the Indiana University Student Health Center followed by measures of weight, body composition, and pulse wave velocity performed at the School of Public Health at Indiana University Bloomington (**Visit 2**). During this visit they will also perform two 6-minute walking tests, and muscle function test. After baseline assessments **Visits 1-2**, participants will be randomly assigned to one of two study arms. All study arms will complete an 8-week exercise training protocol. The first arm will serve as a control group and will require participants to only complete the 8-week exercise training protocol (EX). The second arm will complete exercise training with ingestion of a beetroot (BR+EX). Exercise training will occur no more than 6 weeks following baseline Visit 2 to minimize the effects of potential changes in physical conditioning/deconditioning on baseline measures. Subjects will be asked to repeat baseline Visit 2 before initiating exercise training in the event >6 weeks lapses from the completion of the final baseline assessment visit.

The same procedures as performed in **Visits 1-2** will be repeated following the treatment intervention for **Visits 3-4** in reverse order. The procedures outlined for **Visit 2** will be performed during **Visit 3**, and procedures for **Visit 1** for **Visit 4**.

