**Blood Oxygen Concentrations-** To monitor the concentrations of oxygen and methemoglobin in the blood both prior to and following acute beetroot juice ingestion, a fingertip pulse oximeter will be used (Masimo SpMet). Measurements of SpMet will be taken once every hour for 3-hours following ingestion of beetroot juice during **Visits 1 and 4**. A concentration of SpMet  $\geq$  12% indicates a serious adverse response to acute beetroot supplementation.

**Beetroot Juice Administration-** Participants randomized to receive exercise training and beetroot juice will be supplied with 140 mL of commercially-available beetroot juice (James White Drinks, UK) containing approximately 12 mmol of nitrate. Participants will be given a 4-week supply (24 bottles) which will then be repeated at the half-point of the exercise training progression. Participants will be instructed to consume the supplement between 2 to 3 hours prior to each exercise session to ensure training coincides with peak nitrate/nitrite bioavailability (14). Participant adherence will be determined at random, prior to exercise (on-site), during weeks 3 and 6 using a portable breath analyzer to monitor the fractional exhaled nitric oxide (NIOX MINO, NC) (17).

**Dietary Recall Assessment-** Participants will be asked to record all food, beverages, and supplements that they consumed within a 24hr period on six separate occasions using a paper handout supplied to them (see dietary recall handout in protocol attachments). They will be asked to record three times on one weekend and one weekday during the first week, and again during the last week of the 8Wk supervised exercise training sessions. They will be asked to complete the recalls within a 7-day period at both timepoints. Since this is not a primary outcome variable of interest, and will simply be used to describe amounts of dietary nitrate

consumed outside of the beetroot juice supplement, any subject who does not complete one or more of the recall entries will not be withdrawn from the remainder of study procedures. Subsequent analysis to obtain measures of food group equivalencies for nitrate containing food items (e.g. dark leafy greens) will be conducted using a validated Automated Self-Administered 24h (ASA24) dietary recall system. Approved study personnel will manually enter food, beverage, and supplement items into the electronic recall system to generate a report of dietary characteristics for each 24hr period.

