If participants miss (do not attend) a scheduled exercise training session, they will resume training at the next available scheduled session. The missed workout session will be recorded. Participants will be withdrawn from the study if they miss more than 3 consecutive exercise training sessions in any given week. Additionally, they must complete a minimum of 70% of the total 24 exercise training sessions (17 out of 24 sessions attended) to continue with follow-up assessments.

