### **11.0 Study Withdrawal/Discontinuation**

A subject may elect to discontinue with study procedures by verbally notifying a member of the research team that they would like to do so either in person or by phone. Contact information for [name] and [name] is provided in the Informed Consent Statement. All

members associated with the research study (i.e. fitness instructors at Crossfit Bloomington) will be instructed to notify the research team in the event of a subject dropout.

Subjects may be withdrawn from the study by members of the research team if it is determined their safety is at risk (e.g.  $>20$  mm Hg drop in systolic blood pressure with acute beetroot juice ingestions), they are unable to perform procedures as requested, or fail to follow instructions provided. Additionally, subjects may be withdrawn if they miss (do not attend) more than 3 consecutive exercise training sessions in any given week of the supervised exercise training protocol. Withdrawal is also warranted if they attend less than 70% of the scheduled exercise training sessions (e.g. less than 17 out of the 24 total sessions).

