### **12.0 Statistical Considerations**

Rather than confirm efficacy, this proposal addresses elements of feasibility such that we intend to generate preliminary effect sizes for a larger-scale investigation. Descriptive statistics and calculation of rates (e.g., recruitment, retention, adherence, and adverse event) will be used for study aim 1. Between-group differences in descriptive data along with aims 2(a,b) and 3 will be evaluated using an unpaired t-test. Effect size calculations will be performed with Cohen's  $d$  to qualify substantive differences: small (0.2), medium (0.5), and large (0.8). Potential covariates of interest include age, body mass, body fat percentage, and/or markers of inflammation. Non-normally distributed data will be log-transformed. Two-tailed parametric correlations (Pearson) will be performed and based on consequent results, multiple linear regression will be used to examine changes in inflammation, endothelial function, distance in 6-minute walk test, leg strength, and resting blood pressure/arterial stiffness.

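### The 17-of-24 attendance condition for follow-up means that the Aim 2 and 3 effect sizes would compare adequate attenders only, not all women as randomised

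*Combined protocol and SAP*

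**What the plan says.** Section 5.0 places allocation after the baseline visits and before training: "participants will be randomly assigned to one of two study arms". Under Supervised Exercise Training in Section 7.0, women "must complete a minimum of 70% of the total 24 exercise training sessions (17 out of 24 sessions attended) to continue with follow-up assessments". Section 11.0 uses the same cut-off in softer terms: "Withdrawal is also warranted if they attend less than 70% of the scheduled exercise training sessions".

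The Aim 2 and 3 outcomes are measured at baseline and after the intervention (Sections 3.2 and 3.3). Sections 5.0, 7.0 and 8.0 together place the post-intervention 6-minute walk, pulse wave velocity and blood draw at Visit 3, and cutaneous vascular conductance at Visit 4. Both visits come after the attendance cut-off. Section 3.2 also names "A non-invasive technique of flow mediated dilation of the brachial artery using ultrasound imaging", but no visit is assigned to it, so nothing is claimed about it here.

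Section 12.0 gives the analysis: "Between-group differences in descriptive data along with aims 2(a,b) and 3 will be evaluated using an unpaired t-test", with Cohen's d. It names no analysis set and no method for missing outcomes. It gives the purpose as follows: "we intend to generate preliminary effect sizes for a larger-scale investigation".

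The dietary recall text in Section 7.0 says that "any subject who does not complete one or more of the recall entries will not be withdrawn from the remainder of study procedures". That concerns a descriptive measure and settles nothing about attendance. No corresponding sentence exists for women who attend too few sessions.

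**The concern.** Attendance is observed after allocation. Using it to decide who is measured turns a randomised comparison into a comparison of those who attended enough in each arm. An effect among adequate attenders is a legitimate target for a pilot, but Section 12.0 does not declare it. Measuring everyone would still allow it to be estimated, whereas the attendance condition allows nothing else. Because the rule governs data collection, no later choice of analysis can undo it.

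What is at stake is how the effect sizes will be used. If the larger trial is analysed as randomised (an assumption, since the protocol does not say), it will include low attenders, and the pilot would hold no outcome data on such women. Section 2.1 says that "in the context of this proposal, feasibility is unknown", so the share below the cut-off cannot be predicted.

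**Working it through.** **1. The plan's own figure.** 0.70 × 24 = 16.8, so the smallest qualifying count is 17 (17/24 = 70.8%; 16/24 = 66.7%). The stated 17 reproduces.

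**2. How many women might be excluded.** The documents give no attendance rate. If each session is attended independently with probability a, the chance of fewer than 17 of 24 is binomial:

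| a | share below 17 | of 24 women | of 36 women |
|---|---|---|---|
| 0.70 | 43.5% | 10.4 | 15.7 |
| 0.75 | 23.4% | 5.6 | 8.4 |
| 0.80 | 8.9% | 2.1 | 3.2 |
| 0.85 | 2.0% | 0.5 | 0.7 |
| 0.90 | 0.2% | <0.1 | 0.1 |

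The steps below use 4 of 24 and 6 of 24 as illustrations. The 20-of-24 criterion in Section 3.1 is a success threshold. It does not cap losses, and it does not define completion as 17 sessions. The total of 36 comes from Section 6.0 (4 participants × 9 waves).

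**3. Change of population, with equal loss by arm.** Let p be the share below the cut-off and f the fraction of the attenders' effect that low attenders gain, assumed to lie between 0 and 1:

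as-randomised d = d among attenders × (1 − p(1 − f))

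- d = 0.5, p = 4/24: 0.5 × (1 − 0.167) = 0.417 at f = 0, and 0.5 at f = 1.
- d = 0.5, p = 6/24: 0.5 × (1 − 0.25) = 0.375 at f = 0, and 0.5 at f = 1.
- d = 0.2: 0.167-0.20 and 0.150-0.20 respectively.

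For a two-sample t-test at 80% power and two-sided 5%, d = 0.5 needs 64 per arm, 0.417 needs 92 and 0.375 needs 113.

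**4. Between-arm bias, with unequal loss.** Assume no true effect, 12 randomised per arm, the lowest attenders lost, and a correlation r of 0.3-0.5 between attendance and outcome change. If a fraction k is kept, the mean attendance score of those kept is m(k) = φ(z)/k, where z is the (1 − k) normal quantile. The spurious d is about r × (m(k₂) − m(k₁)), in favour of the arm that lost more.

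- 10 v 10: m is the same in both arms, so the shift is 0.
- 11 v 9: 0.077 at r = 0.3 and 0.128 at r = 0.5. Simulation gave 0.077 and 0.135.
- 12 v 8: 0.164 and 0.273. Simulation gave 0.161 and 0.273.
- 6 of 24 lost (simulation): 0 at 9 v 9, 0.07-0.13 at 10 v 8 and 0.24-0.40 at 12 v 6.
- 6 of 36 lost (simulation): 0 at 15 v 15, 0.05-0.09 at 16 v 14 and 0.16-0.27 at 18 v 12.

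**5. How likely those splits are if loss is unrelated to arm (4 of 24).** The total number of ways is C(24,4) = 10,626.

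- 2/2: 66 × 66 / 10,626 = 41%.
- 3/1 in either direction: 2 × 220 × 12 / 10,626 = 50%.
- All four from BR+EX: 495 / 10,626 = 4.7%.

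About 91% of splits therefore give a spurious d of at most about 0.13 in size. All six of six from BR+EX has probability C(12,6)/C(24,6) = 0.7%.

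**6. Sampling error.** The 95% half-width for d is about 1.96 × √(1/n₁ + 1/n₂): 0.88 at 10 v 10, 0.90 at 12 v 8, 0.98 at 12 v 6 and 0.72 at 15 v 15. Each exceeds the bias illustrated for the same total loss.

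**The case against.** The strongest reply is that this is a feasibility pilot and Section 12.0 disclaims confirming efficacy. The primary rates can still be calculated on every randomised woman. That stands, and it limits the point to the secondary and exploratory aims.

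A second reply is that measuring low attenders would add little precision. Two v two gives a half-width of 1.96, three v three gives 1.60, and moving from 10 v 10 to 12 v 12 only narrows 0.88 to 0.80. A planner could also apply the bounds in step 3 from attendance records alone. This too is fair: the gain is a comparison that keeps the randomised groups, not a precise effect in low attenders.

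A third reply is that one sentence declaring adequate attenders as the target would suffice. It would cure the silence in Section 12.0, but the outcome data would still not be collected.

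A reader might go further and infer that the rule biases the trial towards BR+EX. The documents do not support that. The rule and the training are the same in both arms, everyone drinks the juice at Visit 1 before allocation, and nothing suggests arm-related loss.

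A reader might also see a contradiction between Sections 7.0 and 11.0 on the 70% rule. The cut-off is identical and the difference is mostly one of tone.

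**Conclusion.** The point holds as a matter of design. If the attendance condition in Section 7.0 is followed, the Aim 2 and 3 effect sizes describe women who reached 17 sessions rather than all women as randomised, and the missing outcomes cannot be recovered. This needs no assumption about bias.

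Its size does rest on assumptions. With one in six or one in four below the cut-off, an attenders' d of 0.5 could correspond to as little as 0.42 or 0.38 as randomised, or to no reduction at all. Between-arm bias remains possible but unshown. It is zero under equal loss by the same mechanism, about 0.08-0.13 for 11 v 9, and smaller than the sampling error. The larger figures for 12 v 8 and 12 v 6 need splits that are unlikely unless loss depends on arm. The primary feasibility aim is unaffected. The change is worth making because it is cheap and the lost data cannot be collected afterwards.

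**What to change.** - **Sections 7.0 and 11.0:** separate stopping training from stopping data collection, so that low attendance alone does not end follow-up. Invite every randomised woman to the outcome visits already defined, with priority to Visit 3, unless she withdraws consent or the protocol's own safety or inability provisions (Sections 10.0 and 11.0) apply. Those provisions should cover Visit 3, which includes walking tests and maximal knee extensions, as well as Visit 4. Visit 4 includes an acute juice dose, so the sponsor should state how its procedures apply to women who stopped training.
- **Section 12.0:** make the main Aim 2 and 3 analysis all randomised women with outcome data, as allocated. Make the subset attending at least 17 sessions a secondary analysis. Report staff withdrawals separately from voluntary dropouts, by arm.
- **Wording:** reconcile Sections 7.0 and 11.0 on the attendance rule. Reconcile also the rule on missing more than three sessions in a row within one week. It does not fit three scheduled sessions a week, and it is mandatory in Section 7.0 but discretionary in Section 11.0. This wording point carries no weight in the conclusion.

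**Cost:** one set of existing visits per low attender who agrees. That is about 4 sets per 24 randomised, or 6 per 36, if one in six falls below the cut-off, and more if attendance is worse. Some women may decline, and the effect sizes may come out smaller.

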## **8.0 Study Calendar**

(Screening Visit) After obtaining consent, subjects will be asked to complete a health history questionnaire, risk factor stratification document indicating their readiness to exercise, and provide information to obtain permission to contact their primary care physician. Their age will be verified by a member of our research team by having them provide a valid photo ID (e.g. driver's license), and current prescription medications will be verified by having them bring-in their medication bottles or labels. A measure of height and weight (via BIA) will be obtained to verify BMI inclusion criteria of 25.0 to 39.9 kg/m^2.

(Visit 1) All procedures during this visit will take place at the School of Public Health, Indiana University Bloomington. Measures of height, weight (BIA), body composition (BIA/DEXA), total body water (BIA), and bone density (DEXA) will be taken after having participants change into a provided standard set of hospital scrubs. The remaining procedures will be conducted with the participant resting quietly on a reclining couch. They will be outfitted with a chest-strap electrocardiograph monitor for the duration of the visit. Two laser Doppler probes will be attached to their non-dominant forearm while a localized heating protocol is initiated. A blood pressure cuff will be affixed to their dominant upper arm and blood pressure will be assessed after 5 min of seated rest, and at every 10 minutes of the 30-minute heating protocol. Following, they will perform a breath analysis to measure pre-ingestion levels of exhaled nitric oxide before ingesting 140mL of a commercial beetroot juice supplement. During a 3-hour window following ingestion, participants will be given a rest period and asked to complete a set of two questionnaires. During this time, blood pressure and methemoglobin using a fingertip pulse oximeter will be assessed once every hour. They will be asked to perform an additional breath analysis 3-hour post-ingestion to coincide with estimated maximum nitric oxide bioavailability provided by the supplement. After which, a repeat of the localized heating protocol and blood pressure measurements will be performed.

(Visit 2) A venous blood sample will be collected at the Indiana University Student Health Center. Following, all remaining procedures will take place at the School of Public Health, Indiana University Bloomington. Participants will again, be asked to change into a provided

standard set of hospital scrubs so that accurate measurements of body weight (BIA) and composition (BIA) can be obtained. They will then be asked to lie supine while resting quietly for a period of 10 minutes on a padded table while measures of pulse wave velocity are obtained. They will then be escorted to the recreational track within the School of Public Health building to complete the 6-min walking test and muscle function test.

(8-weeks Supervised Exercise Training) After being randomized into either an exercise only (EX) or beetroot and exercise (BR+EX) group, subjects in the BR+EX group will receive a 4-week supply of beetroot juice. They will additionally be asked to attend 3 sessions of supervised exercise training at CrossFit, Bloomington for a duration of 8 weeks. Subjects in BR+EX will be instructed to consume the beetroot juice 3 hours prior to each attended exercise session.

(Visits 2-3) The remaining follow-up visits will follow the exact same procedures as outlined for Visits 1-2 and will be performed in the reverse order.

	Screening	Initial Assessments		Exercise Training Intervention	Follow-up Assessments	
	Time point 0	Visit 1 (as scheduled)	Visit 2 (following  7-day washout period)	0 to 8 weeks (following £ 6 weeks)	Visit 1 (following  2 days)	Visit 2 (following  2 days)
STUDY PROCEDURES						
Obtain Consent	X					
Medical History Questionnaire	X					
ACSM Risk Factor Stratification	X					
Obtain Permission to Contact Physician	X					
Verification of Age (driver's license)	X					
Prescription Medication Verification	X					
Height	X	x				X
Body Weight (BIA)	X	x	X		X	X
Body Fat Percentage (BIA)		X	X		X	X
Total Body Water (BIA)		X	X		X	X
DEXA		X				X
Heart rate (Actiheart)		X		X		X
Localized Heating Protocol using Laser Doppler		X				X
Blood Pressure		X				X
Nitric Oxide Breath Analysis		X		X		X
Acute Administration of Beetroot Juice (140 mL)		X				X
Blood Oxygen/ Methemoglobin Oximetry		X				X
Questionnaire (Part A and B)		X				X
Venous Blood Draw			X		X	
Pulse Wave Velocity			X		X	
Submaximal Walk Test			X		X	
Heart rate (chest-strap)			X		X	
Accelerometry			X		X	
6-minute Walk Test			X		X	

Rates of Exertion (continuous analog scale)			X		X	
Rates of Exertion (discrete analog scale)			X	X	X	
Isokinetic Dynamometry			X		X	
Supervised Exercise Training Sessions				X		
24hr Dietary Recall				X (3 during week 1 and 3 during week 8 of supervised exercise training)		

